## **Sensitivity Analyses**

We will describe dropout (defined as entering the store but not completing the purchasing task) by study arm. Dropout is defined as passing the screener survey but not completing the exit survey (i.e., dropping out during the shopping task or during the exit survey). If differential dropout is identified, we will consider sensitivity analyses to handle missing outcome data, such as inverse probability weighting. We will compare the main effects to the primary results if the number of participants excluded from a moderation analysis because of missing demographic data warrants it.

For all analyses, all pairwise comparisons of means will be examined for all outcomes. We will consider a result statistically significant at  $p < 0.05$ .

In exploratory analyses, we will examine whether any of the collected participant characteristics (see list below) moderate the intervention effects on the primary outcomes:

- a. Age
- b. Gender
- c. Region
- d. Education
- e. Race
- f. Household monthly income
- g. Household size
- h. Parent/caregiver
- i. Marital status
- j. Experience with online shopping for clothes, electronics, furniture, or home appliances
- k. Experience with online grocery shopping
- l. Hunger levels at time of survey
- m. BMI
- n. Self-reported health status
- o. Diabetes
- p. Heart disease

To test whether these characteristics moderate the effect of each intervention on nutrient content, we will fit a series of regression models (one for each potential moderator), with trial arm, the moderator (specified as dummy variables), and their interaction as predictors. We will use a Wald chunk test to determine the joint significance of the interaction terms. We will quantitatively evaluate the presence of moderation by calculating the marginal effect of each intervention on the outcome at different levels of the moderating variable. If the pattern of main results is similar between intervention arms (magnifying glass label based on ANVISA nutrient profile model, magnifying glass label based on PAHO nutrient profile model), we will consider combining intervention arms for the moderation analysis.

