### *Secondary Outcomes*

The secondary outcomes are the percentage of ultra-processed products purchased (as defined by the NOVA classification), perceived healthfulness of unhealthy products, perceived product appeal of unhealthy products, concern about health effects of unhealthy products, ability to identify high sugar/saturated fat/sodium content of unhealthy products (as per the PAHO nutrient profile model, which is stricter than ANVISA's), and noticing of the product label.

We hypothesize that, compared to the no-label control, the ANVISA magnifying glass condition and PAHO magnifying glass condition will lead to:

1. Lower percentage of ultra-processed products (as defined by the NOVA classification) purchased.
2. Lower perceived healthfulness of unhealthy products.
3. Lower perceived product appeal of unhealthy products.
4. Higher concern about health effects of unhealthy products.
5. Higher ability to identify high sugar/saturated fat/sodium content of unhealthy products.
6. Higher noticing of the front-of-package label.

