## **STATISTICAL CONSIDERATION**

### **Statistical Methods**

The study is a randomized controlled trial. The analysis will rely on random assignment to identify the effect of each type of front-of-package label nutrient profile model on consumer choices.

We will conduct a soft launch with 100 participants to check randomization and data quality. If randomization is working properly and there are not apparent issues with the data collection, we will resume data collection until the final sample is achieved. The original participants from the soft launch will be included in the final dataset. If randomization is not working properly (as assessed using the tabs command in Stata) and/or there are apparent issues with the data collection (e.g., erroneous skip patterns), we will address all identified issues then resume data collection until the final sample is achieved.

We will descriptively report unadjusted values for primary and secondary outcomes. We will use a two-sided critical alpha of 0.05 to conduct all statistical tests. Per CONSORT guidelines, we will not test for balance in covariates. Primary analyses will be intent-to-treat, including all eligible participants with non-missing data for the outcome being analyzed.

For all primary, secondary, and other outcomes, we will assess whether the outcomes vary by study arm. For the primary outcomes, we will use two-sample t-tests for means. If there are imbalances in potentially

confounding factors between arms, we will use linear regressions. For the secondary and other outcomes, we will use linear regression.

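### Merging the two label arms for moderation when their main results look alike uses the wrong trigger: similar average effects do not imply similar moderation (minor; exploratory analysis only)

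*SAP*

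**What the plan says.** The moderation analysis is exploratory and confined to the primary outcomes: "In exploratory analyses, we will examine whether any of the collected participant characteristics (see list below) moderate the intervention effects on the primary outcomes". Sixteen characteristics are listed, with one regression per characteristic containing arm, moderator and their interaction.

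The aim is set separately for each label: "To test whether these characteristics moderate the effect of each intervention on nutrient content". The test is joint: "We will use a Wald chunk test to determine the joint significance of the interaction terms". Moderation is then to be described by "calculating the marginal effect of each intervention on the outcome at different levels of the moderating variable".

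The paragraph ends with an exception. The condition is "If the pattern of main results is similar between intervention arms", and the consequence is that "we will consider combining intervention arms for the moderation analysis". The SAP does not say what counts as similar, which of the three primary outcomes must agree, or whether the interactions are to be looked at first. The Secondary Outcomes section describes the PAHO model as stricter than ANVISA's ("as per the PAHO nutrient profile model, which is stricter than ANVISA's").

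**The concern.** The condition looks at one quantity and the decision concerns another. Two labels can reduce mean sugar by the same amount while one works mainly in, say, people with diabetes and the other works evenly. Similar main results cannot tell that case from one where pooling is harmless.

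Merging replaces the two arm-by-moderator interactions with their average. A moderator that acts on one label only then appears at half its size, and equal and opposite interactions cancel. A null result from the merged arm could be read as no moderation of either label. Because similarity has no criterion, the choice would also be made after the effects are known.

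**Working it through.** **The plan's own figure.** The Sample Size and Power section claims at least 90% power for certain main-effect comparisons. It gives no pilot means or SDs, so the claim cannot be reproduced; it can only be inverted. With 3,000 participants, a 6% loss and 1:1:1 allocation (assumed, as the ratio is not stated), n = 3000 × 0.94 / 3 = 940 per arm. The detectable difference is √(2/940) × (1.960 + 1.282) ≈ 0.150 SD. No power is given for any interaction, so what follows shows relative behaviour only.

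**Inputs.** Two-sided alpha of 0.05 comes from Statistical Methods ("We will use a two-sided critical alpha of 0.05 to conduct all statistical tests"). Three arms and the joint Wald test come from Sensitivity Analyses. Equal arms, a two-level moderator and 80% power for the three-arm test are assumptions.

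**Set-up.** Let the moderator's extra effect be 0 in control, 1 in one label and r in the other, in arbitrary units.

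- Three-arm test (2 df): noncentrality is proportional to A = 1 + r² − (1 + r)²/3.
- Merged test (1 df): the interaction is (1 + r)/2, and noncentrality is proportional, with the same constant, to B = (2/3) × ((1 + r)/2)².

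For each r, the three-arm noncentrality is fixed at 9.63, which gives 80% power on 2 df. The merged noncentrality is then λ = 9.63 × B/A, and merged power is Φ(√λ − 1.96) + Φ(−√λ − 1.96).

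| r | A | B | B/A | λ merged | Three-arm power | Merged power |
|---|---|---|---|---|---|---|
| 1 (identical) | 0.667 | 0.667 | 1.00 | 9.63 | 80% | 87% |
| 0.5 | 0.500 | 0.375 | 0.75 | 7.22 | 80% | 77% |
| 0.25 | 0.542 | 0.260 | 0.48 | 4.63 | 80% | 58% |
| 0 (one label only) | 0.667 | 0.167 | 0.25 | 2.41 | 80% | 34% |
| −0.5 | 1.167 | 0.042 | 0.036 | 0.34 | 80% | 9% |

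**Break-even.** The 1-df test has 80% power at λ = (1.960 + 0.842)² = 7.85, so B/A must be 7.85/9.63 = 0.815. At r = 0.57, A = 0.503 and B = 0.411, giving 0.816. Merging therefore gains power only when the weaker interaction is at least about 57% of the stronger.

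**Second route, on the plan's sample size.** Take 940 per arm, a moderator with 50% prevalence, residual SD 1 and an interaction of 0.3 SD in one label only. Each arm's moderator slope has variance v = 1/(940 × 0.25) = 0.00426.

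- Three-arm: noncentrality 0.09 × (2/3)/v = 14.1, power 93%.
- Merged: noncentrality 0.15²/(1.5v) = 3.53, power 47%.

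A simulation of 4,000 trials gave the same 93% and 47%. At 20% prevalence the figures are 77% and 32%; at 10%, 51% and 20%. If instead both labels are moderated by 0.2 SD at 50% prevalence, merging raises power from 60% to 71%.

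**Does the trigger discriminate?** The simulations gave both labels the same true main effect. Taking a non-significant difference between the labels as a stand-in for similarity, about 95% of runs passed, both when one label was moderated and when the two were moderated in opposite directions. The trigger did not respond to the difference in moderation.

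**The case against.** The case for leaving the rule alone has substance. The moderation work is labelled exploratory, as is the whole study in Sample Size and Power. Merging needs a condition to be met and is then only to be considered; the three-arm model is the default. Both labels use the same magnifying-glass format, so moderation in the same direction is plausible, and merging costs little at r = 0.5 and gains above about 0.57. The SAP gives no interaction estimates, so neither the favourable nor the unfavourable cases can be called typical. All of this stands, and it limits the weight of the point.

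Three stronger readings are tempting, but the document does not support them.

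- **That merging defeats the study's purpose, namely the difference between the labels.** The stated purpose is the impact of different nutrient profiles on choices, and every listed hypothesis compares a label with no label. ANVISA against PAHO appears only under the all-pairwise comparisons and in the power statement for ultra-processed products.
- **That the paragraph contradicts itself.** The label-specific effects belong to the default model, and the merge is an explicit exception to it. The label-specific effects are lost only if the exception is used.
- **That power would fall to 34% or 9% in this trial.** Those figures depend on an assumed 80% starting point and particular patterns of moderation.

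What the objection does not answer is that the trigger examines main effects when the decision depends on interactions, and that the benefit of merging is available without merging.

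**Conclusion.** The concern holds as a minor one. Similar main results do not justify merging for moderation, and a merged arm cannot supply the marginal effect of each label. Under equal arms, a two-level moderator and an assumed 80% power for the three-arm test, merging gains at most 7 points (identical moderation), loses 3 at r = 0.5, 22 at r = 0.25, 46 when only one label is moderated, and 71 at r = −0.5. The halving of a one-label interaction is algebra once the arms are equal; the power figures depend on the assumptions. No primary or secondary comparison with control is affected.

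**What to change.** Make the three-arm interaction model, the joint Wald test and the label-specific marginal effects the moderation analysis for every moderator, whatever the main results show. Replace the conditional merge with a supplementary contrast, labelled as such: the interaction for the average of the two labels against control, taken from the same fitted model. With equal arms its variance is v + v/2 = 1.5v, the same as for the merged arm, so essentially all the precision of merging is kept and no choice is left until after the results are seen.

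The change is to SAP wording and needs no new data. The cost is at least 16 moderators × 3 primary outcomes = 48 extra exploratory contrasts, and more if moderators with several levels are reported level by level. The SAP sets 0.05 for all tests and states no multiplicity adjustment, so these contrasts should be reported as supplementary estimates with intervals, not as separate claims of significance.

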## **Sample Size and Power**

This is an exploratory study and the sample size was maximized at 3,000 participants. Data from a pilot study of 300 participants conducted in December 2022 and January 2023 showed that, accounting for a loss of 6% of participants after excluding the top 2% of values for total saturated fat, sodium and sugar, 3,000 participants would provide at least 90% power to 0.05-level two-sided t-tests for mean differences between ANVISA and the control in total saturated fat and sugar, between PAHO and the control in total saturated fat, and between each arm in the proportion of ultra-processed products checked out (equal and unequal variances).

## **Outliers and Exclusions**

We will examine detailed summary statistics on each continuous outcome measure and exclude observations with unrealistically high values (e.g., in the top 2% of values). Separately, we will also conduct sensitivity analyses excluding individuals who are in the bottom 2 percentile of the expenditures, those who complete the study unusually quickly (e.g., based on the distribution of time to completion of ascertained during a soft launch of the study), and individuals who are non-compliant with the shopping list (<50% of products selected comply with the shopping list).
